7.2 Study Timeline

Year		1				2				3				4	
Quarter		1	2	3	4	1	2	3	4	1	2	3	4	1	2
Project- months	Pre-grant start	3	6	9	12	15	18	21	24	27	30	33	36	39	42
Trial Stage	Using Enabling Grant Award	Set	up		Recruit	ment and Follow-up			Follow-up				Analysis and Reporting		
Pilot study with implantation of 4 OriLens devices	x X														
Identification of six potential sites	x														
Protocol Development and finalising of Trial Manual after trial of four participants	×														
Training Pack development and collation including surgical movie	×														
R&D Approvals		Х	Х												
Site Training		Х	Х	Х											
Main Study					Х	Х	Х	Х	Х						
Number of sites open			5	8	10	10	10	10	10	10	10	10	10		
Participant Recruitment				10	20	40	80	120	132						
Participant Follow up				Х	Х	Х	Х	Х	Х	Х	Х	Х	Х		
Interim Analysis							Х								
stop & go POINT (safety)							Х								
Data Collection (including HRQoL)			Х	Х	Х	Х	Х	Х	Х	Х	Х	Х	Х		
Management Meetings		XXX	XXX	XXX	XXX	XXX	XXX	XXX	XXX	XXX	XXX	XXX	XXX	XXX	XXX
DMEC		Х		Х			Х		Х				Х		Х
TSC		Х		Х			Х		Х				Х		Х
Trial Close Down (sites)														Х	Х
Data Analysis														Х	Х
Health Economics Analysis														Х	Х
Trial Report														Х	Х
Dissemination															Х

Table 1: MIRROR STUDY TIMELINE

7.3 **Project Milestones**

The duration of the study will be 42 months. A maximum of 10 centres will be required for the study with each site recruiting approximately 13-14 participants. As training will be required in participant selection, visual function testing, surgical implantation, and the use of the telescope, the study investigators would prefer to open eight sites only. However, if recruitment is not progressing to target, consideration will be given to opening new sites. The first six months will be spent on study setup, recruitment of staff, and in the initiation of surgical and low vision training of staff at all sites. A period of 18 months has been allocated for the recruitment phase (months seven to 24). Twelve months follow-up will be required after recruitment of the last subject and six months for analysis of data and dissemination of results including report writing and submission of papers. Project recruitment will be measured to determine that the target sample of 132 is achievable with the number of recruiting sites indicated.

8 Methods: participants, interventions, and outcomes

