8.4 Outcomes

8.4.1 Primary Outcome

The primary outcome is change in BCDVA at 12 months after randomisation using number of letters improvement on ETDRS as measured by a masked independent assessor. Visual acuity will be assessed as indicated in the Trial Manual. BCDVA can be a variable endpoint depending on the assessor. In order to reduce variability, participants can be encouraged to read to achieve their best visual acuity. BCDVA at the 12 month time point will initially be measured by the optometrist on the research team. An independent assessor will then repeat the BCDVA at the 12-month time point and this measurement will be used for the primary analysis. Refraction will be carried out by the optometrist on the research team prior to the independent assessment and the independent assessor will be instructed not to look directly into the participant's eyes. As an additional measure, the trial frames will be placed on the participant by the research optometrist, which will aid masking.

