8.4.2 Secondary Outcomes

• Clinical outcomes:

1. Change in best-corrected near visual acuity (BCNVA), reading speed and contrast sensitivity from baseline.

• Health Economic Outcomes:

- Health related quality of life measured using EQ-5D-5L at randomisation, six and 12 months (17)
- 2. Vision-specific quality of life measured using Impact of Vision Profile (IVI) at randomisation, six and 12 months (18)
- 3. Health service use and associated costs measured at six months and 12 months
- 4. Participant out-of-pocket costs measured at six months and 12 months.
- **Safety of the device:** The safety of device will be assessed postoperatively by noting any surgical complications during or after surgery and at each subsequent visit, including any reduction in visual acuity, position of the device, and corneal clarity. The endothelial cell density will be assessed at baseline and at 12 months (13-16).

• Mechanistic evaluation:

- 1. Correlation of participant ocular parameters such as scar size and volume with outcomes
- 2. Correlation of Preferred Retinal Locus (PRL) and ocular dominance with outcomes
- 3. Evaluation of the role of binocularity and visual summation on outcomes.

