8.6 Sample Size

As little information is available on improvement with secondary telescopic implants in pseudophakic eyes, the power calculations were based on improvements in BCDVA in participants with advanced AMD undergoing cataract surgery. Assuming from the previous IMT study that the telescope is capable of providing a 10 letter improvement for BCDVA from baseline and that standard care i.e., cataract surgery without the magnifying device will improve visual acuity by a mean (SD) of 1.94 (13.4) letters, 59 participants in each group would be required to detect a 8.06 letter difference between the two groups at 90% power, giving 66 per group accounting for 10 attrition (3, 8).

The power for the study is based on a minimum improvement of 10 letters expected from the telescope. This is in keeping with other studies such as the FDA-approved IMT study (3). However, as this is a comparative study with comparison to standard care i.e., cataract surgery with routine type IOL insertion, the difference expected will be eight letters. The choice of an eight letter difference is justified as follows:

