10.6.2 Statistical methods

The primary endpoint is the change from baseline of BCDVA at the 12-month time point in the study eye. The treatments will initially be compared using the independent t-test followed by a repeated measures analysis of covariance, adjusting for site, baseline BCDVA as a covariate and other covariates/factors where appropriate. Possible covariates/ factors will be discussed in the Statistical Analysis Plan (SAP) and may include size of scar, thickness of scar, and ocular dominance. Statistical diagnostic methods will be used to check for violations of the model assumptions and data transformations or non-parametric equivalents such as Mann-Whitney may be performed as appropriate. The primary data at 12 months are the BCDVA measurements by the independent assessor. The 12 month BCDVA data measured by the optometrist on the research team will be analysed as part of a sensitivity analysis.

The continuous secondary endpoints will be analysed in the same manner as the primary endpoint with an endpoint specific baseline covariate term included.

Analyses will be two-sided and tested at an a priori significance level of p=0.05. The primary time point has been defined as the 12-month time point. There is no adjustment for multiple testing at the different time points, as the primary outcome has been defined and prioritised.

For the mechanistic evaluation, descriptive statistics will be used to present the results. Also, the relationship between visual outcome and several factors (as discussed in Section 7.1) will be investigated using the independent t-test, 1-way analysis of variance, Pearson's correlation coefficient or non-parametric equivalents as appropriate depending on the scale of measurement of the factors.

Inter-rater reliability between the independent assessor and the optometrist on the research team will be tested for BCDVA at 12 months using the intra-class correlation coefficient.

Baseline characteristics, follow-up measurements and safety data will be described graphically and in tabular format using appropriate descriptive summary measures depending on the scale of measurement and distribution.

A detailed SAP will be written by the trial statistician prior to the final analysis.

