11.2 Interim analyses

In order to assess recruitment progress, an internal pilot study will be undertaken to assess feasibility which will run until month six of the recruitment period (month 12). By this time, it is anticipated that 20 participants will have been recruited and all sites will have been opened.

At the end of the pilot, the following analysis will be completed:

- Recruitment rate: % recruited versus target recruitment number
- % randomised based on total number screened

Recruitment feasibility milestones will be as follows: If recruitment rates achieve 75-100%, the trial will progress. If only 50-75% recruitment is achieved, the trial will progress following review of screening logs and the protocol and once barriers to achieve adequate recruitment are addressed. If 25-50% of the required number are recruited, the trial will progress only after screening logs and the protocol are reviewed and once, following approval by NIHR-EME, additional sites are opened. Should recruitment be <25%, it is not expected that the trial will progress; this decision will be made by the TSC.

An interim analysis will also be conducted to analyse efficacy and safety parameters. In relation to efficacy, an independent t-test will be applied with a *p* value <0.001 according to the Haybittle-Peto stopping rule. For safety, intraoperative complications are not anticipated to be significant. There is a potential risk of corneal endothelial cell damager in those who have been implanted with the device. Therefore, corneal clarity will be assessed at each clinic visit.

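### The month-18 efficacy interim falls before essentially anyone has the 12-month primary outcome, and Section 11.2 does not say which BCDVA reading its p<0.001 test would use

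*Protocol*

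**What the plan says.** - **Interim rule (Section 11.2).** "An interim analysis will also be conducted to analyse efficacy and safety parameters". Efficacy is to be tested with an independent t-test at p<0.001, citing Haybittle-Peto. The section gives no outcome time point, calendar date or information fraction. For safety it names possible corneal endothelial damage and designates corneal clarity, checked at each visit, as the monitor.
- **Interim date (Section 7.2, Table 1).** The single mark in the interim analysis row is in the month-18 column. The row "stop & go POINT (safety)" is marked in the same column.
- **Recruitment (Section 7.3 and Table 1).** "A period of 18 months has been allocated for the recruitment phase (months seven to 24)". Cumulative targets are 10, 20, 40, 80, 120 and 132 at months 9, 12, 15, 18, 21 and 24.
- **Primary outcome (Section 8.4.1).** "The primary outcome is change in BCDVA at 12 months after randomisation", measured by a masked independent assessor. Section 10.2.2 puts the visit at about 12 to 13 months. Sections 8.2.7, 8.4.1 and 10.3 provide that assessor at month 12 only.
- **Cell density (Section 8.4.2).** "The endothelial cell density will be assessed at baseline and at 12 months".
- **Final test (Section 10.6.2).** "Analyses will be two-sided and tested at an a priori significance level of p=0.05".

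**The concern.** The protocol itself fixes a test, a threshold and a date for an efficacy look. Together these cannot be applied to its primary endpoint, because the 12-month outcome does not yet exist at the scheduled date.

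The DMEC would then have two options. It could skip an analysis that the protocol promises, or it could run the t-test on an earlier visit. The second option means choosing an endpoint during the trial and basing a stopping recommendation on readings by assessors who can see the device. The masked 12-month assessment was added to guard against exactly that weakness. Moving the look later does not restore its purpose: by the time the 12-month data could say much, there is nobody left to recruit or implant.

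**Working it through.** **1. The plan's own sample size.** Section 8.6 states that "59 participants in each group would be required to detect a 8.06 letter difference between the two groups at 90% power", and that standard care "will improve visual acuity by a mean (SD) of 1.94 (13.4) letters". With n per group = 2 × [SD × (z₀.₉₇₅ + z₀.₉₀) / difference]²:

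2 × [13.4 × (1.960 + 1.282) / 8.06]² = 58.1, rounded up to 59.

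Allowing for attrition, which I read as 10%: 59 / 0.90 = 65.6, rounded up to 66 per group, 132 in total. The plan's figures are reproduced. Exact t-test power at 59 per group is 90.0%.

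**2. Checking the reading of Table 1.** Section 11.2 expects 20 recruited by month 12. That agrees with the 20 in the month-12 column, so the columns are read correctly.

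**3. How many 12-month outcomes exist, and when.** Accrual starts at the beginning of month 7 and is taken as linear between the Table 1 targets (an assumption). A 12-month outcome is counted once a participant is 12 months past randomisation, or 13 months for the figure in brackets. Counts are before attrition.

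| Project month | Recruited | 12-month BCDVA available |
|---|---|---|
| 18 | 80 | 0 (0) |
| 19 | about 93 | about 3 (0) |
| 21 | 120 | 10 (about 7) |
| 24 | 132 | 20 (about 17) |
| 29 | 132 | about 67 (about 53) |
| 30 | 132 | 80 (about 67) |

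Half of the planned outcomes (66) are reached at about month 29 (month 30 with the 13-month visit). The last implantation can fall eight weeks after the last randomisation (Section 7.1): month 24 plus about 1.8 months, or about month 26.

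Section 8.7.1 describes recruitment differently, as about 21 months after a three-month lag. If that means randomisation from month 4, some 3 to 5 participants could have a 12-month reading at month 18.

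**4. What else exists at month 18.** On the same accrual, about 17 to 20 participants have a 6-month BCDVA (visit at 6 to 7 months) and about 38 have a 3-month BCDVA (visit at 14 weeks). All of these are site optometrist readings.

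**5. Chance of crossing p<0.001.** Noncentral t, two-sided, n per arm, difference 8.06, SD 13.4. Standard error = 13.4 × √(2/n); noncentrality = 8.06 / standard error; observed difference needed = critical t × standard error.

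| n per arm | Standard error | Noncentrality | Critical t | Difference needed | Power |
|---|---|---|---|---|---|
| 5 | 8.47 | 0.95 | 5.04 | 42.7 letters | 0.5% |
| 10 | 5.99 | 1.34 | 3.92 | 23.5 letters | 1.6% |
| 20 | 4.24 | 1.90 | 3.57 | 15.1 letters | 6.4% |
| 33 | 3.30 | 2.44 | 3.45 | 11.4 letters | 17.1% |

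The row for 10 per arm applies both to 6-month data at month 18 and to 12-month data at month 24. The row for 20 per arm approximates 3-month data at month 18. The row for 33 per arm is the look at 66 outcomes. Using the 12-month effect and SD at earlier visits is an assumption; the protocol gives no other values.

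**6. Committee dates.** After month 18, Table 1 next shows the DMEC at month 24, when the recruitment target is met, and then at months 36 and 42.

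**The case against.** Several points on the other side stand.

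- **The endpoint is not stated.** Section 11.2 does not tie the t-test to month 12, and BCDVA is also taken at months 1, 3 and 6. A reader might infer that the test would have no data at all; that is not so. But the data available are not the primary outcome and were not obtained by the masked assessor, and the protocol nowhere says that an earlier visit is meant.
- **Recruitment is still open when the first 12-month data arrive.** A reader might infer that recruitment and implantation are finished as soon as any such data exist. They are not: at month 21 about 7 to 10 outcomes exist with 12 participants still to recruit, and implants can continue to about month 26. The supported statement is that both are over before the 12-month data become informative.
- **The safety look can work.** A reader might infer that the month-18 stop/go fails because post-implant cell density is taken only at month 12. Section 11.2 names corneal clarity as its interim monitor, and complications and adverse events are collected at every post-operative visit. Section 11 also explains the month-12 count by the time at which cell loss usually stabilises.
- **Low power is not a fault in itself.** A p<0.001 boundary is meant to respond only to extreme effects, and it costs negligible type I error. The final analysis at 0.05 and the sample size are unaffected.
- **Some detail could go in a SAP or DMEC charter.** The time point and information fraction could. The date and the test, however, are fixed in the protocol, and no later document can supply month-12 outcomes at month 18.

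**Conclusion.** Wrong as written; should be fixed. The efficacy interim as scheduled cannot be run on the primary endpoint: 0 of 132 outcomes at month 18 on the Section 7.3 dates, or at most about 3 to 5 if Section 8.7.1 is read as randomisation from month 4. Run on 6-month readings instead, it would use an unmasked substitute with about a 1.6% chance of crossing at the design effect. On 12-month data, the chance stays under 2% until recruitment closes and reaches about 17% only at months 29 to 30, after the last implantation.

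The counts rest on recruitment meeting the Table 1 targets with linear accrual between them; slower recruitment would leave fewer outcomes at any given date. The power figures rest on the design difference and SD. The problem is confined to the efficacy test. It does not undermine the safety stop/go, the sample size or the final analysis.

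**What to change.** Preferred: remove the efficacy t-test and the Haybittle-Peto rule from the month-18 look in Section 11.2 and make that look safety-only. List what the DMEC will have (complications, corneal clarity, adverse events and early BCDVA as a safety measure), and state that little or no 12-month cell density will be available. Relabel the interim analysis row in Table 1 to match its stop/go row, which is already marked as safety.

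Alternative, if an efficacy look is kept: name the endpoint as the masked 12-month BCDVA, trigger the look by a stated number of those outcomes rather than a calendar month, and acknowledge that an informative look falls after recruitment closes. Say also what a crossing would then lead to.

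Either option is a wording change to Section 11.2, Table 1 and the DMEC charter. Neither changes the sample size or the final significance level, and dropping the look gives up no analysis that could have been run on the primary outcome as scheduled.

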11.3 Definition of Adverse Events

As the current study is not investigating medical products, adverse event reporting will follow the Health Research Authority guidelines on safety reporting in non CTIMP studies. The PI or designee will make an assessment of seriousness as per the definitions below:

An **adverse event (AE)** is defined as any untoward medical occurrence in a participant in a research study, including occurrences which are not necessarily caused by or related to the study.

A serious adverse event (SAE) is defined as an untoward occurrence that:

- a) results in death;
- b) is life-threatening;
- c) requires hospitalisation or prolongation of existing hospitalisation;
- d) results in persistent or significant disability or incapacity;
- e) consists of a congenital anomaly or birth defect; or
- f) is otherwise considered medically significant by the investigator.

*Hospitalisation is defined as an inpatient admission regardless of length of stay, even if the hospitalisation is a precautionary measure for continued observation. Hospitalisations for a preexisting condition, including elective procedures that have not worsened, do not constitute an SAE.

b.4 Anticipated adverse events due to implantation of the OriLens

Below is a list of potential or anticipated Adverse Events based on prior IMT clinical trials or known to be occasionally associated with similar types of anterior segment surgery. This list should not be considered comprehensive, but rather identifies events which can be reasonably anticipated.

- Acute corneal decompensation
- Anterior segment neovascularizion
- Choroidal detachment
- Corneal oedema
- Cystoid macular oedema
- Endophthalmitis
- Fibrin in the anterior chamber
- Hyphema
- PC IOL dislocation
- OriLens device dislocation
- Inflammatory deposits on OriLens device
- Intraocular inflammation
- Iris transillumination defects
- Optic atrophy
- Posterior synechiae
- Removal of OriLens device
- Repositioning of OriLens device

11.5 Eliciting Adverse Event Information

- Retinal vascular occlusion
- Anterior chamber cells
- Anterior synechiae
- Corneal transplant
- Cyclitic membrane
- Distorted pupil
- Epithelial heaping
- Flat anterior chamber
- Hypopyon
- Increased IOP requiring treatment
- Iris atrophy
- Iritis
- Pigment deposits on OriLens device
- Pupillary block
- Requirement for iridectomy/iridotomy
- Retinal detachment
- Secondary glaucoma

The PI or designee will record all directly observed AEs and all AEs spontaneously reported by the participant that are not related to underlying medical conditions. In addition, the participant will be asked about AEs at day one, day seven, and months one, three, six and 12 following implantation of the device.

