8.5 Participant Timeline

Eligibility will be determined at the screening visits. Surgery in Group 1 will take place at Day 0 with surgical review on days one and seven and study visits for both Groups at months one, three, six and 12. As the presence of the device is obvious to the casual observer, it will not be possible to mask assessors. Participants can also not be masked to the intervention. However, the final BCDVA measurement at 12 months will be duplicated by an additional observer independent to the trial and this measurement will be used for the primary analysis. BCDVA (primary outcome) will be measured with 4-meter ETDRS charts. Assessment at screening will include medical history, ophthalmic examination, confrontation visual field testing, visual acuity, reading speed, refraction, contrast sensitivity, assessment with x2.5 external telescope for distance and near vision, assessment for ocular dominance, binocular visual function, endothelial cell density, ocular coherence tomography (OCT) with volume scan, colour fundus photography, IVI, and EQ-5D-5L. Fundus fluorescein angiography (FFA) will be carried out in addition to OCT at baseline and only subsequently if clinically indicated as OCT cannot be performed post implantation of the device. The order of screening examinations will follow as per Figures 3 and 4, however, this may vary at site depending on the location of equipment. The detailed schedule is shown below in Table 2.

If all inclusion criteria are met at both screening visits, participants will be enrolled into the study. The required clinical information will be returned to the lead site (NICTU) and the study eye will be selected. The participant will be informed within 72 hours regarding which eye has been selected as the study eye and will be provided with a date to attend for Nd:YAG capsulotomy in the study eye, if not already done. After the participant has undergone the laser treatment, the Principal Investigator (PI) or designee will contact the CTU to determine group allocation. The participant will then be notified within 72 hours post laser treatment regarding group allocation.

Group 1 Care Pathway:

- Day 0: Surgery (surgical implantation of OriLens device)
- Day 1: Surgical review
- Day 7: Surgical review
- Assessments will be carried out at Months 1, 3, 6 and 12
- Low vision training at months 1, 3 and 12

Group 2 Care Pathway

- Day 0: No procedure

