11 METHODS: MONITORING

b.4 Assessment of safety

The safety of device will be assessed at each visit by noting any surgical complications during or after surgery, including visual acuity, position and clarity of the device and corneal clarity. From previous studies it is known that loss of corneal endothelial cells following implantation of devices such as this is often biphasic i.e., there is an initial decrease following surgery then a continued loss for some months but at a lower rate. Stabilisation usually occurs at 12 months (13-16). The corneal endothelial count will therefore be repeated at month 12. It is not anticipated that the device itself will cause any systemic adverse events. A record will be kept of all Serious Adverse Events (SAEs). The CI will be responsible for informing the Sponsor, the Research Ethics Committee and all study sites about any SAEs. The DMEC will provide information on all SAEs on a routine basis.

b.4.1 Analysis of safety data

Adverse events (AEs, SAEs) will be listed and summarised by treatment. Incidents will be listed and summarised by treatment. Responses to the recent falls question will be tabulated. Endothelial cell densities will be listed.

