11.6 Recording of Adverse Events

All AEs will be assessed for seriousness, expectedness and relatedness by the PI or designee, recorded in the CRF and notified to the CI/trial manager once the PI becomes aware of the AE. All AEs will also be recorded in the participant's medical notes.

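### Section 11.5 filters spontaneously reported adverse events by cause before they are recorded, contradicting sections 11.3 and 11.6 of the protocol

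*Protocol*

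**What the plan says.** Section 11.5 of the protocol sets out three ways in which an AE reaches the record:

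- Direct observation: "The PI or designee will record all directly observed AEs".
- Spontaneous report, with a restriction: "all AEs spontaneously reported by the participant that are not related to underlying medical conditions".
- Active questioning: "In addition, the participant will be asked about AEs at day one, day seven, and months one, three, six and 12 following implantation".

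Section 11.3 defines an AE as any untoward medical occurrence in a participant, "including occurrences which are not necessarily caused by or related to the study". Section 11.6 then states: "All AEs will be assessed for seriousness, expectedness and relatedness by the PI or designee, recorded in the CRF". The safety analysis paragraph in section 11 lists and summarises AEs and SAEs by treatment, and section 4.3.3 puts AEs in the report to the data monitoring committee.

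**The concern.** Under 11.3 and 11.6, cause is something to be assessed for each AE once it is on record. Under 11.5, for one route of reporting, cause decides whether the event is recorded at all. The protocol does not define an underlying medical condition and makes no exception for the disease under study. Every participant has advanced AMD in both eyes (section 8.2.2), so a volunteered complaint of worse vision or distortion fits the exclusion literally once a site attributes it to AMD.

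The site makes that attribution knowing the allocation. Section 9.4 accepts that observers cannot be masked, and the only protected measurement is the independent 12-month distance acuity. The same complaint might be taken as a possible device effect in one arm and as the natural course of AMD in the other. Safety is a secondary objective, and the by-treatment AE summary is where such a difference would show. A non-serious event that was never written down may not be recoverable at analysis.

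**Working it through.** No figure in the protocol bears on this point, so the check is a comparison of sections.

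**1. Do the sections conflict?** Take a participant who telephones between visits to report blurring that the site attributes to AMD.

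- Section 11.3: an AE, because cause plays no part in the definition.
- Section 11.6: an AE, so it is assessed for relatedness and entered in the CRF.
- Section 11.5: volunteered and related to an underlying condition, so outside what the site is told to record.

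The first two require an entry and the third does not. The contradiction is on the page.

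**2. Which reports does the restriction reach?** On its natural reading the restriction attaches only to spontaneous reports. The sentence on directly observed events has no such limit, nor does the sentence on questioning. Section 11 keeps a record of all SAEs, again without exception for underlying disease, and item (f) of the SAE definition in 11.3 lets the investigator class any event as serious if considered medically significant.

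**3. What would catch an AMD-related event by another route?**

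- Table 2 and section 10.2.2 schedule medical history, distance acuity and ophthalmic examination in both groups at months 1, 3, 6 and 12. The Table 2 footnote includes fundoscopy in that examination.
- Fundus photography is repeated in both groups at month 12.
- Section 8.4.2 makes a reduction in acuity part of the safety assessment at each subsequent visit.

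**4. What remains exposed?** An event that is non-serious, volunteered rather than elicited, not directly observed by staff, and attributed to an underlying condition. Section 11.8 runs AE reporting from enrolment to month 12. In Table 2 the intervention group has AE checks at days 1 and 7 and months 1, 3, 6 and 12, which is six. Controls have the last four only, the first at about 6 to 8 weeks after randomisation. No check falls between months 6 and 12 in either group. In those gaps spontaneous reporting is the main route, unless the event is raised again at the next visit.

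**5. Do the questioning times agree?** Section 11.5 counts them from implantation, which controls do not have. Table 2 and 10.2.2 schedule the checks for both groups from month 1, so the schedule is clear and the wording of 11.5 is loose.

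**6. Falls.** The safety analysis says "Responses to the recent falls question will be tabulated". That question is not named in Table 2, in the visit list in 10.2.2 or among the instruments in 10.3, so the protocol does not say when it is asked.

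**The case against.** The strongest reply is that 11.5 is a clause of limited reach, probably meant to keep background illness out of the AE forms, and that 11.6 in any case requires all AEs to be recorded. The events of most concern have other scheduled routes, as shown above, and acuity in the study eye is itself the primary outcome. This stands as a limit on the size of the problem. It does not remove the contradiction: 11.5 is the instruction on what to record from participants' reports, and a site following it has grounds to leave the event out.

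Three stronger readings are tempting, and the protocol does not support them.

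- A reader might infer that all participant-reported events, or AMD reactivation as such, are removed at source. They are not, because elicited, observed and serious events are outside the restriction.
- A reader might infer that the imaging limit makes this a major gap in the implant arm. Section 8.5 repeats FFA "only subsequently if clinically indicated as OCT cannot be performed post implantation of the device", so symptoms may carry more weight in an implanted eye. But Table 2 schedules OCT and FFA at screening only, in both groups, so scheduled follow-up imaging does not differ on this account. The OCT limit belongs to the device, and rewording 11.5 would not alter it.
- A reader might infer that the falls table will be empty or lack a baseline. The CRF, the trial manual and the resource use questionnaire are not shown, and the question may sit in one of them. Its responses are also tabulated separately from the AE listing, so the restriction in 11.5 need not touch them.

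**Conclusion.** The point holds as an internal contradiction with a limited but real consequence for safety reporting. Section 11.5 conflicts with 11.3 and 11.6, and following it can lose non-serious, volunteered, AMD-attributed events on an unmasked judgement that may differ between arms.

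The wording applies to all 132 planned participants, but the number of events lost cannot be estimated. The protocol gives neither a rate for such events nor the share that would be volunteered and never observed or elicited. The direction of any distortion is equally unknown.

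The conclusion assumes that the restriction qualifies spontaneous reports only and that AMD counts as an underlying medical condition. The first is the natural reading. The second follows from the plain words, since AMD is not excepted. The questioning times and the placing of the falls question are lesser matters of wording and schedule.

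**What to change.** - In 11.5, delete the clause that limits spontaneous reports to those unrelated to underlying conditions. All AEs in both arms are then recorded, and relatedness is judged afterwards under 11.6.
- In the same section, replace the reference to time since implantation with the AE checks in Table 2: months 1, 3, 6 and 12 for both groups, and days 1 and 7 for the intervention group.
- As a separate minor edit, state in Table 2 and 10.2.2 the visits at which the recent falls question is asked, and of which group.

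The contradiction does not require new event categories or a new falls schedule. The cost is somewhat more AE entries for sites and data management. No visit or procedure is added, and clinical management is unchanged. The edit should be made before recruitment starts, because events left out under the present wording may not be recoverable later.
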